## STUDY SUMMARY

---

**Background:** This is a pilot randomized clinical trial (RCT) study to demonstrate the feasibility and acceptability of a transition in care strategy to improve retention in HIV care and antiretroviral therapy (ART) adherence for ex-inmates in South Africa. Our prior studies have identified the need for a retention in care strategy by documenting the substantial attrition in HIV care following release from corrections to the community. Our approach is informed by a conceptual model of key barriers to the care transition developed from our prior work along with a behavioral explanatory model, the Behavioral Model for Vulnerable Populations.

The overarching goal of this study is to tailor and pilot a transition community adherence club (TCAC) strategy for HIV-positive individuals transitioning from correctional to community settings in South Africa. CACs represent an accepted HIV care delivery approach that is currently available to “stable” HIV patients in South Africa. CACs provide medication refills, a brief health screen, and health discussions in a group setting. Observational studies have found that CACs are more acceptable, lead to fewer missed visits and shorter visit times without queueing, and increase engagement in care. Improving engagement in care for HIV-positive ex-inmates could have an important impact on the HIV epidemic in South Africa, a country with the 11th highest global corrections population and an estimated HIV prevalence of 23% in corrections settings.

**Aims:** The aims of the study are to pilot a randomized clinical trial of a transition community adherence club (TCAC) versus traditional care to study feasibility, acceptability, and preliminary effectiveness using mixed methods.

**Methods:** This project is a pilot randomized clinical trial (RCT) to refine and test the feasibility, acceptability, and preliminary effectiveness of the TCAC. At the conclusion of the R34 grant period we will have a protocol and procedural manual ready for a full RCT powered for effectiveness.

**Significance:** The proposed study is consistent with NIH HIV/AIDS highest priority research and the South African National Strategic Plan on HIV, TB, and STIs 2017-2022. The research addresses the HIV/AIDS Research Priority of “retention and engagement in these services, and achievement and maintenance of optimal prevention and treatment responses.” It also addresses “health disparities” through a focus on recently released inmates, a marginalized population. The proposal also fits with the South African National Strategic Plan prioritizing inmates as a key population for HIV services.

## Glossary of Terms

---

AIDS	Acquired Immuno-deficiency Syndrome
ART	Antiretroviral Therapy
CAC	Community Adherence Club
CAU	Care as Usual
CBO	Community Based Organization
CCD	Community Corrections Department
CCMDD	Central Chronic Medicine Dispensing and Distribution (system or service)
CRF	Case Report Form
DCS	Department of Correctional Services
DOH	South African Department of Health
HIV	Human Immunodeficiency Virus
LT FU	loss to follow up
NIH	National Institutes of Health
PHC	Primary Health Clinic
PIS	Participant Information Sheet
RCT	Randomized Clinical Trial
SA	South Africa
STI	Sexually Transmitted Illnesses
TB	Tuberculosis
TCAC	Transition Community Adherence Club

## 1 INTRODUCTION

---

### 1.1 Background

**HIV care in corrections:** Inmates in most of the 240 correctional facilities in South Africa have on-site access to HIV care provided by the Department of Correctional Services (DCS). Voluntary HIV testing is provided at facility entry, routinely during testing 'campaigns,' and in the corrections clinics. In addition, as per South Africa HIV treatment guidelines (2016), all inmates living with HIV were eligible for ART regardless of CD4 count. Within the correctional facilities, care engagement and adherence to medication are supported by inmate peer educators and inmate support groups. At the time of release from corrections, inmates are provided a referral letter that briefly summarizes their HIV care history and current medications. Inmates are released with between 15 and 90 days (median 30 days) supply of ART ([name] unpublished data).

**Barriers to the transition from corrections to community care:** Post-release, ex-inmates are expected to use the referral letter to establish care with Department of Health (DoH) clinics. It is the responsibility of the ex-inmate to identify the clinic and the appropriate days to go, and to advocate for his or her care. There is no active follow-up provided by DCS or DoH to confirm a successful transition, nor is there specific coordination between the DCS and the DoH regarding the release of ex-inmates receiving HIV care. Because of the absence of formal communication between the DCS and the DoH there is no documentation of the transition of care from corrections to community care to inform patient care, care continuum indicators, or quality improvement. The impressive HIV care outcomes observed in correctional settings in South Africa drop off dramatically following release from corrections. Ex-inmates living with HIV encounter unique care transition challenges across the socio-ecological framework. Qualitative and quantitative research conducted by the PI ([name]) and co-I ([name]) with 492 ex-inmates in South Africa, identified several important themes related to the transition in care among ex-inmates. These include the clinic experience, social capital, stigma, substance use (11% of participants with identified drug use), re-incarceration, and economic insecurity. Depression also affects the transition from corrections to community care in the United States, but has not been evaluated in this context in South Africa. Substance use is another barrier to the care transition. Substance use itself interferes with care seeking due to increased impulsivity as well as diminished social capital. As a result of these barriers, at 6-months following release, only 44% had continuity in antiretroviral therapy ([name] unpublished data).

**Barriers to care engagement in the general population in Africa:** Experience with the general population living with HIV provides additional insight regarding potential barriers for ex-inmates. On the individual level of the socio-ecological model, knowledge of HIV, self-efficacy, fatalism,

and depression are all positively or negatively associated with care engagement. On the interpersonal level, a network of supportive ties can assist with material and psychosocial support and provide encouragement to attend clinic, leading to increased engagement in care. This type of supportive network can be characterized as individual (or micro) bonding social capital. On the community level, enacted stigma is also associated with lower linkage to care and ART uptake. On the clinic level clinic enacted stigma compromises retention in care because people tend to avoid places associated with stigmatization. The combination of HIV stigma and ex-inmate stigma may be especially challenging for men who were diagnosed with HIV during incarceration and return from corrections marked by both stigmas. Stigmatization appears to be especially insidious in regard to the care continuum when it occurs at the clinic where the negative effect on engagement in care is stronger than from stigma experienced in the community or family. Additional clinic level factors that are barriers include long waiting times, frequent visits, and the need to start queuing early in the morning.

**Transitional Community Adherence Clubs:** During follow-up focus groups with these ex-inmates, several solutions were suggested to facilitate the transition from corrections to community care including non-stigmatizing support groups or community adherence clubs (CACs) composed of individuals with similar experiences, assistance with locating skills training or starting a job search, and more efficient and non-stigmatizing care. CACs represent an accepted HIV care delivery approach that is currently available to “stable” HIV patients in South Africa. Community adherence clubs provide medication refills, a brief health screen, and health discussions in a group setting. Observational studies have found that CACs are more acceptable, lead to fewer missed visits and shorter visit times without queueing, and increase engagement in care. A tailored CAC for ex-inmates transitioning in care, here termed a transition community adherence club (TCAC), has the potential to simultaneously address multiple barriers at the individual, interpersonal, and care delivery levels.

## 1.2 Study objectives

The overarching goal of this study is to tailor and pilot a transition community adherence club (TCAC) strategy for HIV-positive individuals transitioning from correctional to community settings in South Africa. The current proposal will allow for developing and piloting of the TCAC strategy to assess the feasibility for a fully powered effectiveness randomized clinical trial (RCT) comparing the TCAC to traditional care with a primary outcome of being in care with an undetectable viral load six months after release.

The primary objectives of this study are:

1. To assess the feasibility of implementing TCACs and of endpoint ascertainment

2. To assess the effectiveness of TCACs compared to care as usual by the differences in proportions of self-reported care at six months following corrections release.
3. To assess the acceptability of TCACs to ex-inmate participants and to implementing staff

The secondary objectives of this study are:

1. To assess the effectiveness of TCACs compared to care as usual with regards to:
  - Verified in care at six months
  - Time to linkage to care
  - Linkage to care within 90 days of corrections release
  - HIV RNA <400 c/mL at six months
  - Social capital score change
  - Stigma index score change
  - Employment or self-employment

### 1.3 Significance

This study fits with the South African National Strategic Plan prioritizing inmates as a key population for HIV services, particularly the priority of care continuity for this population. The study is also consistent with NIH HIV/AIDS highest priority research and the South African National Strategic Plan on HIV, TB, and STIs 2017-2022. The research addresses the HIV/AIDS Research Priority of “retention and engagement in these services, and achievement and maintenance of optimal prevention and treatment responses.” It also addresses “health disparities” through a focus on recently released inmates, a marginalized population.

## 2 METHODS

---

### 2.1 Study design

This is a pilot randomized clinical trial (RCT) to refine and test the feasibility, acceptability, and preliminary effectiveness of TCACs.

### 2.2 Study setting

This pilot operational research study will be conducted in Gauteng Province. Recruitment will occur within correctional facilities of the Department of Correctional Services (DCS) (expected Kgosi Mampuru II and Modderbee). The activities within the correctional facilities and in the Districts will build on ongoing Aurum Institute service delivery and research projects.

All study interventions will occur following release in either Ekurhuleni District, Tshwane District or Johannesburg District.

### 2.2.1 Correctional Facilities

Kgosi Mampuru II Correctional Centre is sub-divided into 4 centres namely: awaiting trial offenders sentenced male offenders, sentenced female offenders, and a maximum security centre. The Correctional Facility has a population of approximately 8,900 offenders. Modderbee Correctional Centre is sub-divided into 3 centres namely: awaiting trial offenders, medium security centre and a maximum security centre. The correctional facility has an estimated population of 6460 offenders. It also has two satellite centres (Devon and Nigel Correctional Centres) that accommodate inmates who are about to be released and those who have short to mid-term sentences, respectively. In all the selected study facilities, each centre has its own primary health clinic (PHC) which provides TB treatment services, and in addition, different sections share one main hospital in which the ART clinic is located and where ART patients receive care. Offenders from each section are allocated a specific day in the week to attend the ART clinic in an effort to avoid mixing of offenders from different centres.

### 2.2.2 Description of the geographical areas of study implementation

**Ekurhuleni District:** This is one of the 6 districts of Gauteng province of South Africa and the fourth largest Metropolitan municipality in South Africa. The district had an approximate population of 2.8 million people (City of Ekurhuleni Annual Report 2010-2011). In the last HIV antenatal survey conducted in 2010, Ekurhuleni had the highest HIV prevalence in the province (34.0%) compared to other districts (Department of Health, 2010).

**Tshwane District:** This is one of the 6 districts of Gauteng province of South Africa and includes Pretoria. The total population of Tshwane is 2.9 million people.

**Johannesburg District:** This is one of the 6 districts of Gauteng province of South Africa. The total population is 4.4 million and total area is 1,645 km^2.

### 2.2.3 Rationale for selecting geographical areas of study implementation

We selected the correctional facilities based on a long-standing working relationship between the PI, Aurum Institute, and these facilities. This has included a prior study of linkage to care following corrections release and health systems strengthening work. The districts have been selected because they are the three districts to which the majority of inmates from these correctional centers are released to.

## 2.3 Study Population

The population is comprised of adult ( $\geq 18$  years old) corrections inmates, either male or female, with known HIV infection and are receiving ART within the correctional facility and are expected to be released back into the community within 3 months of study enrollment.

### 2.3.1 Inclusion criteria

- Currently incarcerated (either an offender (sentenced inmates) or awaiting trial inmate (un-sentenced))
- Housed at Modderbee or Kgosi Mampuru II Correctional Centres (including participating satellite centres)
- Diagnosed with HIV
- Currently receiving ART
- Anticipated release or trial date within 3 months of study enrollment
- Self-report expected to reside within Ekurhuleni, Tshwane, or Johannesburg districts of Gauteng Province and within proximity to one of the TCAC sites (within 20km, 45 minute travel time, or two local taxi minibus rides)
- Agree to post-discharge follow-up
- Medically stable based on DCS health assessment
- On ART for  $>3$  months at the expected time of corrections release

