#### 2.4.2 Randomization

We will perform individual randomization blocked by correctional facility. Study staff will open numbered envelopes with the allocation following enrollment. Participants will be randomized 1:2 to either the standard of care or the TCAC using sequential envelopes with study arm determination sealed inside (blocked by study site and based on random number generation). Participants and members of the research team recruiting and implementing the strategy will be unmasked to randomization assignment due to the behavioral nature of the strategy and need for team members to explain the study arm procedures to participants. Study assignments will be masked to staff performing outcome assessments and the investigators until all outcome data have been collected.

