## 2.7 Post release follow-up

The tracing of participants will primarily be based on the tracing plan developed with the participant during the in-correctional facility contact sessions (Appendix A: AD001 Locator and Tracing Plan). The tracing plan will contain information on alternative addresses at which the participant anticipates staying after release, if they plan to be at the same address in 3 months and 6 months, names and contacts of next of kin (part of informed consent), telephone numbers, and study staff contact information. After the participant has been released, study staff will also liaise with Community Corrections Department (CCD) staff to obtain extra information on where the participant is actually released to. The following strategies for tracing will be performed:

- Participants will be educated to telephonically contact a study team member within 15 days of release; for which they will receive a small incentive in the range of a ZAR 20 - 50 (US\$3-7) airtime vouchers. Offenders will be instructed to send “call-me” messages to an allocated study cell-phone number that the case manager can access and respond to, thereby making the calls free for the ex-offenders.
- In the event that participants fail to initiate contact, study staff will use available contact information from the tracing plan or CCD staff to contact released offenders at the determined follow-up time points.
- If no contact is made via participant or study staff initiation, the case worker will work with CCD staff (who have contact details for all paroled individuals) to contact the released offender.

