### 4.2.2 Effectiveness

Effectiveness will be based on intention to treat comparing CAU and intervention group outcomes using assessed using mixed effects logistic regression with correctional facility included as a mixed effect.

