### 5.3.5 Study limitations

The proposed implementation research has the following limitations:

- The study depends on contact with incarcerated individuals following release. Such individuals may be more likely to come from unstable living situations and may be highly mobile, making follow up a challenge. However, our experience is that released offenders seek re-integration services and are required to provide accurate contact information for the purposes of compliance with parole. Thus we anticipate tracing a high percentage of released offenders.
- Participant self-report regarding lapses in medications and entry into care may introduce bias as participants may favour the most socially acceptable responses. Verification of self-reported entry-into-care using clinic records will be conducted, where possible, for all participants. Data abstraction forms will be submitted to health staff at the health centres

where participants will report to have linked (refer to out-of-correctional facility clinic data abstraction form).

- Follow up and observation of participants in the pre-intervention period (more frequent than current standard of care) may result in modified or improved participant outcomes because of the fact that they are being studied.
- Pre/post assessments that we intend to apply in this study are susceptible to secular trends and to differences in outcome ascertainment. We believe that secular trends in HIV care both in DCS centers and in the public sector will be minimal in terms of HIV care in correctional centers, care in the community, and the offender population. To account for potential population differences we will include disease state and personal characteristics in the logistic regression analysis.
- A low proportion participating would markedly reduce the generalizability of the results (pre and post-intervention). Our experience is with an interest and willingness of inmates to participate in studies. Thus we do not anticipate this to be a significant limitation.

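### Legal status (sentenced or awaiting trial) plausibly affects release and tracing, but it is absent from the effectiveness model and the feasibility indicators

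*Combined protocol and SAP*

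**What the plan says.** **Who enters.** Section 2.3 describes inmates "expected to be released back into the community within 3 months of study enrollment". Section 2.3.1 is wider. It admits "either an offender (sentenced inmates) or awaiting trial inmate (un-sentenced" inmates and asks for "Anticipated release or trial date within 3 months of study enrollment".

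**Allocation and model.** Section 2.4.2 states: "We will perform individual randomization blocked by correctional facility". The ratio is 1:2, care as usual (CAU) to TCAC. Section 4.2.2 specifies "mixed effects logistic regression with correctional facility included as a mixed effect" and names no other covariate; Table 3 lists unadjusted tests. None of the feasibility indicators in Table 2 is split by legal status.

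**Outcome.** Section 2.9.2 analyses self-reported care at 6 months among all randomised individuals, with visits timed from release. A second analysis drops those not released within 3 months and those re-incarcerated, among others.

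**Tracing.** Section 2.7 relies first on an individual tracing plan, participant call-ins and staff contact. If these fail, "the case worker will work with CCD staff (who have contact details for all paroled individuals", that is, Community Corrections staff holding parole contact details. Section 5.3.5 expects a high percentage to be traced for two reasons: released offenders seek re-integration services, and they "are required to provide accurate contact information for the purposes of compliance with parole".

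**The concern.** A trial date is not a release date, so an awaiting-trial participant may be randomised and still be in custody when follow-up should begin. Such a person stays in the all-randomised analysis with an outcome clock that has not started. Nor can someone who leaves from awaiting-trial status be assumed to be on parole, so the last tracing step and the parole argument in 5.3.5 may not reach that person.

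Legal status may therefore act on release, on being found at 6 months and on the primary outcome. Two things are at stake: some precision in the comparison of arms, and what the pilot can tell the full RCT. Endpoint ascertainment is part of the first primary objective, and one pooled follow-up rate cannot show whether awaiting-trial inmates should be enrolled next time.

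**Working it through.** **Inputs from the protocol.** 60 CAU and 120 TCAC released participants; 0.25 against 0.49; alpha 0.05; 78% ascertainment (section 4.1); follow-up target of at least 75% (sections 2.9.1 and 4.2.1). Section 4.1 attaches 0.25 and 0.49 to being in care with an undetectable viral load, not to self-reported care, so they serve here only as an illustration.

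**Inputs assumed, because the documents do not give them.** The awaiting-trial share *w*, its follow-up rate *f*, and the odds ratio linking awaiting-trial status to the outcome.

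**1. The plan's own figure.** Evaluable: 60 × 0.78 = 46.8 and 120 × 0.78 = 93.6. The pooled proportion is (46.8 × 0.25 + 93.6 × 0.49)/140.4 = 0.41.
- SE under the null: √[0.41 × 0.59 × (1/46.8 + 1/93.6)] = 0.0881.
- SE under the alternative: √[0.25 × 0.75/46.8 + 0.49 × 0.51/93.6] = 0.0817.
- z = (0.24 − 1.96 × 0.0881)/0.0817 = 0.825, so power is 0.795. The stated 80% reproduces with a two-sided test.

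**2. Cost of omitting the covariate.** Simulation with 47 against 94 analysed, 6,000 runs per setting, ordinary logistic regression with and without legal status, no facility effect.

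| *w* | Odds ratio | Power without | Power with |
|---|---|---|---|
| 20% | 0.5 | 0.790 | 0.799 |
| 20% | 0.2 | 0.793 | 0.822 |
| 30% | 0.33 | 0.790 | 0.816 |
| 50% | 0.5 | 0.790 | 0.805 |
| 50% | 0.2 | 0.791 | 0.845 |

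Over all nine settings the gain is about 1 to 5 points. Type I error is about 0.04 to 0.05 either way, and the unadjusted risk difference averages about 0.24, its true value.

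**3. Chance imbalance.** The SD of the difference in share between arms is √[*w*(1 − *w*)(1/60 + 1/120)]. For *w* = 20%, 33% and 50% it is 0.063, 0.075 and 0.079, so the chance of a gap of at least 10 points is about 11%, 18% and 21%. The effect is small: with an assumed 20-point outcome gap by legal status, a 10-point imbalance moves the estimate by 0.10 × 0.20 = 2 points, against a standard error of about 8 points.

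**4. Overall follow-up** = (1 − *w*) × 0.78 + *w* × *f*.

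| *w* | *f* | Overall | Power, 0.25 vs 0.49 |
|---|---|---|---|
| 10% | 50% | 75.2% | 0.780 |
| 20% | 60% | 74.4% | 0.775 |
| 30% | 50% | 69.6% | 0.746 |
| 50% | 50% | 64.0% | 0.708 |
| 50% | 40% | 59.0% | 0.671 |

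The expected rate falls below 75% once *w* exceeds (0.78 − 0.75)/(0.78 − *f*): about 8%, 11%, 17% and 38% for *f* = 40%, 50%, 60% and 70%.

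At *w* = one third and *f* = 60%, the overall rate is 0.52 + 0.20 = 72%, and the exact binomial chance of at least 135 of 180 is about 21%. At *f* = 70% it is 0.52 + 0.233 = 75.3%. For comparison, that chance is about 86% at a true rate of 78% and 54% at exactly 75%.

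**The case against.** A reader might infer three stronger things, and the documents support none of them.

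- **That legal status is a known predictor.** No section reports an association with being in care, and the barriers that section 1.1 lists from prior work do not include it. The link is plausible, through release and tracing; it is not established.
- **That the follow-up expectation holds only for parolees.** The individual plan, participant call-ins and staff contact apply to everyone, and clinic records can identify unreported visits (Table 5, FV002). One back-up route and one of two stated reasons depend on parole. The 75% and 78% come from prior work whose legal-status mix is not given, so they may already include awaiting-trial inmates.
- **That omitting the covariate makes the comparison invalid.** Randomisation protects it, and the simulation shows no bias.

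The plan also handles part of the problem. Recruitment continues to 180 released inmates, and the second analysis removes those not released in time or re-incarcerated. Section 5.3.5 promises personal characteristics in the logistic regression, but names none, in a paragraph about pre/post assessments that does not fit this randomised design. Section 4.1 says that this is not an effectiveness study, so a few points of power matter little.

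It is also fair that parole does not coincide with sentenced status: nothing says that every sentenced inmate leaves on parole. That is a reason to report type of release as well. None of this supplies a feasibility result by legal status.

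**Conclusion.** The concern holds in a limited form. Two groups with different entry criteria are pooled, and neither the named model nor the feasibility table separates them. The effect on the comparison of arms is modest: about 1 to 5 power points for assumed odds ratios of 0.5 to 0.2, and no bias.

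The effect on the feasibility conclusion could be larger. Overall follow-up would be about 59% to 74% if 20% to 50% are awaiting trial and are followed at 40% to 60% against 78% for the rest. It could also be negligible: one third followed at 70% leaves it at about 75%. These figures rest on assumed shares and rates, and on applying 78% to the remaining participants, whereas section 4.1 applies it to participants generally. They show what a pooled rate could hide; they do not predict a missed target. This is an inexpensive improvement, not a flaw that threatens the trial.

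**What to change.** 1. In section 4.2.2, prespecify legal status at enrolment as a fixed covariate. First confirm that EL001 or the baseline incarceration history records it: the forms are not reproduced, and since both statuses qualify, eligibility alone does not show that it is captured.
2. In Table 2, add the proportions released and ascertained at 6 months by legal status, and by type of release (parole or not) where recorded. Type of release is known only after randomisation, so use it for description and not as a covariate.
3. In section 5.3.5, limit the parole sentence to paroled participants.

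The cost is analysis-plan wording and a few table rows. If neither form holds legal status, one baseline item must be added.
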